5. STUDY PLAN

See Schema

This randomized, controlled trial is designed to evaluate the effect of acupuncture on CIPN, other symptoms, and potential opioid and concomitant medication sparing effects in comparison to standard of care management in MM subjects. Enrollment in this study should not affect subject care in any way. Subjects will not be reimbursed for study participation; however, the acupuncture treatments will be covered by the study and will be at no cost to the subject. This study will open as a single center study at LCI Morehead.

Potential participants with a transplant in their current MM treatment plan: Subjects may be enrolled in this study either prior to stem cell transplant or after they have completed their transplant. Subjects will be enrolled prior to transplant if they are able to complete the study prior to hospitalization for transplant. Subjects will be enrolled post-transplant if scheduling will not allow them to complete the study prior to hospitalization or transplant. Post-transplant

subjects may enroll when recovered sufficiently from the transplant, i.e. platelets $>50 \times 10^3/\mu\text{L}$, ANC $> 0.5 \times 10^3/\mu\text{L}$, and ECOG performance status is 0-3.

Subjects will be enrolled over approximately twelve months. Each enrolled subject will be on study for approximately 3 to 4 months.

5.1 Study Intervention

Study subjects in the intervention arm will experience acupuncture in a group setting when possible to resemble the conditions of regular clinical practice at Levine Cancer Institute, therefore enhancing external validity and the ability to apply the conclusions of the study to “real-world” contexts outside of the study setting. For as long as COVID-19 is a concern, the acupuncture team will follow these additional safety measures: subjects will be seated at an appropriate distance apart and wear masks, and additional time will be allotted between sessions to allow for additional, thorough cleaning/sanitizing of equipment.

The acupuncture sessions will begin with a more intensive, twice weekly treatment for the first two weeks and taper to once per week for the remaining eight weeks. This amounts to 12 total sessions over approximately 10 weeks.

The acupuncture procedure and specific acupoints will be performed in accordance with the Revised Standards for Reporting Interventions in Clinical Trials of Acupuncture (STRICTA) guidelines⁶⁷ in **Appendix A**.

Consenting and all conversations with subjects regarding their medical history and medications will be held privately. Questionnaires will also be administered privately. All subjects will be able to answer the questionnaires via two options: 1) on paper (in person or via certified mail) or 2) via RedCap electronic survey. Phone contact for questionnaires is acceptable if unable to be completed by other stated routes. The form of questionnaire administration will be based on the appointment situation, needs and/ or preference of the subject, and subject access to technology (e.g., computer, tablet, smartphone). Subject will need to be willing to provide an active email to which the questionnaires can be sent to utilize the electronic survey option.

Subjects randomized to the control arm will have their CIPN treated by their physician per standard of care. Subjects randomized to the intervention arm will begin acupuncture sessions within two weeks of enrollment and will continue their SOC treatment for CIPN as per their physician.

Subjects in both the treatment arm and the control arm will complete the study questionnaires at protocol defined timepoints, even if bortezomib/bortezomib-combination therapy is removed from their treatment regimen during the study (for those on active treatment). Questionnaires should be completed at protocol defined timepoints even if those on the acupuncture arm have not received the acupuncture session on schedule or if sessions are missed.

5.2 Missed Study Assessments

If data from questionnaires are missing, when possible, the reason for the missing data will be categorized and documented as follows:

- subject felt too ill;
- clinician or nurse felt the subject was too ill;
- subject felt it was inconvenient or took too much time;
- subject felt it was a violation of privacy;
- subject didn't understand the actual language or was illiterate;
- administrative failure to distribute the questionnaire;
- not required at this time point;
- other, specify;
- unknown

5.3 Sociodemographics, Medical History, Opioid and Concomitant Medication Intake

The electronic medical record (EMR) will be consulted to abstract demographic, medical history, opioid and concomitant medication data. Subjects will be asked to verify and add any information about their demographics, medical history, opioid and concomitant medications.

5.3.1 Sociodemographics

The sociodemographic information to be collected at baseline only includes:

- Age
- Sex
- Race/ethnicity
- Health insurance type
- Home environment (e.g., lives alone/independent, lives with spouse/partner, lives with children)
- Marital status
- Employment status
- Zip code

5.3.2 Medical History

The medical history information to be collected at baseline only, includes:

- Peripheral (sensory) neuropathy Grade by CTCAE 5.0 criteria⁶⁸ (only if recorded in medical record)
- MM diagnosis date and staging
- ECOG performance status⁶⁹
- Body mass index (BMI) calculated by height and weight
- History of diabetes (excluding gestational diabetes)
- Cardiovascular disease
- Chronic kidney disease
- Vertebral fractures

- Current chemotherapy regimen and all bortezomib/bortezomib-combination treatment given prior to enrollment

5.3.3 Opioid Intake

The electronic medical record will be consulted for opioids in the opioid medication list and verified with the subject. Subjects will be asked if there are any other opioids they are taking which might not be documented in the EMR. This information will be collected at the baseline, midpoint and endpoint visit. Subjects will be asked to provide the information based on a past 7-day recall. The self-reported quantities will be converted to Morphine Equivalent Daily Dose (MEDD), using an opioid conversion calculator (See Appendix B).

These opioids include but are not limited to:

- fentanyl (such as Fentora®)
- hydromorphone (such as Dilaudid®)
- long-acting hydromorphone (Exalgo®)
- oxycodone (such as Oxycontin®)
- oxycodone with acetaminophen (such as Percocet®)
- oxymorphone (such as Opana®)
- hydrocodone with acetaminophen (such as Vicodin®, Hycet®)
- tramadol (such as Ultram®, Conzip®)
- morphine (such as MS-Contin®)
- methadone (such as Methadose, Dolophine®)

5.3.4 Concomitant Medication Intake

The electronic medical record will be consulted for concomitant medications as listed below and verified with the subject. Subjects will be asked if there are any other concomitant medications (including over-the-counter medications) which might not be documented in the EMR. This will be asked and collected at the baseline, midpoint, and endpoint visit. Subjects will be asked to provide the information based on a past 7-day recall.

These concomitant medications include but are not limited to:

Prescription non-steroidal anti-inflammatory drugs

- ketoprofen (such as Actron®, Orudis®)
- celecoxib (such as Celebrex®)
- meloxicam (such as Vivlodex®, Mobic®)

Other prescription medications

- gabapentin (such as Neurontin®, Gralise®, Horizant®)
- duloxetine (such as Cymbalta®)

- pregabalin (such as Lyrica®)
- venlafaxine (such as Effexor XR®)
- amitriptyline, (such as Elavil®, Venatrip®)
- doxepin (such as Silenor®, Zonalon®)
- nortriptyline (such as Pamelor®)

Over the counter non-steroidal anti-inflammatory drugs (no prescription needed)

- aspirin (such as Bayer®, Excedrin®, Bufferin®)
- acetaminophen (such as Tylenol®)
- ibuprofen (such as Motrin®, Advil®, Motrin IB®, Nuprin®)
- naproxen (such as Aleve®)

Topical treatments applied to the skin

- Capsaicin creams
- Lidocaine patches or gel

Note: Collect any other medications the subject identifies for management of CIPN symptoms

5.4 Questionnaires

Questionnaires will be administered privately, preferably **prior** to the acupuncture session for those on intervention arm. All subjects will be able to answer the questionnaires via two options: 1) on paper (in person or via certified mail) or 2) via RedCap electronic survey. Phone contact for questionnaires is acceptable if unable to be completed by other stated routes. The form of questionnaire administration will be based on the appointment situation, needs and/ or preference of the subject, and subject access to technology (e.g., computer, tablet, smartphone).

Questionnaires to be completed at Baseline, midpoint and endpoint visits, even if those on the acupuncture arm have not received the acupuncture session on schedule or if sessions are missed.

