1.1.4 Acupuncture for CIPN in Multiple Myeloma

Acupuncture is a nonpharmacologic practice within Traditional Chinese Medicine that involves the insertion of thin needles at specific sites on the body, known as acupoints, to affect the body's physical function and induce a therapeutic response.²¹ Previous studies show promise for acupuncture's use for peripheral neuropathy in MM,²²⁻²⁵ however, sample sizes have been small and additional studies are needed.²⁶

In 2011, Bao and colleagues reported the first case study of a MM patient who experienced significantly reduced bortezomib-induced peripheral neuropathy (BIPN) after fourteen acupuncture treatments. The patient had significantly reduced neuropathic pain, less requirement for narcotics to treat pain, and improved physical function with minimal side effects.²⁷ Another case study by Mandıroğlu, Çevik, & Ayli (2014) found complete resolution from a BIPN pain score of eight to zero out of ten after six months of acupuncture without any side effects.

This was followed by a case series of five patients of the same population who all received immediate BIPN-related pain reduction after a single acupuncture treatment. Two of the three patients who had at least three acupuncture sessions experienced lasting pain relief and functional improvement after the last acupuncture session. There were no adverse effects.²³ The same author team then pursued a pilot study of twenty-seven MM patients with BIPN resistant to other medical interventions even after bortezomib had been discontinued. Neuropathic pain was significantly reduced and physical function was significantly improved after ten acupuncture sessions over ten weeks.²⁵ A feasibility study of nineteen MM patients with BIPN who were given twenty electroacupuncture sessions over nine weeks found significantly improved pain and physical functioning including walking, buttoning buttons and postural stability.²⁴ A systematic review and meta-analysis of the efficacy of acupuncture for CIPN found that acupuncture can relieve CIPN pain and functional limitations, which warrants larger scale studies.²⁸

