5.4.2 Neuropathy 0-10

The primary outcome measure is subject-reported global ‘neuropathy’ right now, measured on an 11-point scale modeled after the Edmonton Symptom Assessment (ESAS) ⁷⁰ from 0=*no neuropathy* -10= *worst possible neuropathy*. This measure is of unknown validity, although it has been used in previously published studies on CIPN. ^{23,71} For clarity, subjects are provided with a definition of neuropathy with symptom descriptors.

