6. STUDY CALENDAR

Procedures/Assessments	Screening Visit	Baseline (complete within 2 weeks from consent, can be done at screening AFTER Randomization)	Weeks 1-2 ² : Twice per week	Weeks 3-10 ² : Once per week	Week 5 ± 1 week ^{3,5} Midpoint	Week 10 ± 1 week ^{3,5} Endpoint	Early Termination (if applicable) ⁷	Follow Up (30 days [+7] from last Acup tx)
Informed Consent Form	X							
Randomization via CTMS (within 2 weeks from consent)		X ¹²						
Sociodemographics & Medical History (see 5.3.1 and 5.3.2)		X						
Multiple Myeloma status ⁶		X						
ECOG	X							
Height / Weight/ BMI		X						
Acupuncture Expectancy Scale ⁴		X ⁴						
Acupuncture Treatment ^{1,2}			X ²	X ²				
Collect Chemotherapy regimen information ¹⁰	X					X	X	
Adverse Events of Special Interest ⁸			Continuously, starting at First Acupuncture session			X	X ¹³	
CIPN: Neuropathy 0-10 & neuropathy physical location	X ¹¹				X	X	X	
CIPN: FACT-GOG-NTX		X ¹⁴			X	X	X	
Other Symptoms: Constipation, dizziness, dry mouth		X ¹⁴			X	X	X	
Quality of Life: CDC HRQOL-4		X ¹⁴			X	X	X	
Opioid Intake/ Morphine Equivalent Daily Dose (see Appendix B)		X ⁹			X	X	X	
Concomitant Medication: (See Section 5.3.4 for which medications to collect)		X ⁹			X	X	X	

Key to Footnotes

¹ First acupuncture session to occur within 2 weeks of enrollment (date randomized). Acupuncture treatment schedule to start on a Monday or Thursday only.

² Week 1 for subjects on the acupuncture/intervention arm is the week when the first acupuncture session occurs. Window for acupuncture sessions during Week 1 and Week 2 is at least 1 day (minimum) and no more than 8 days (maximum) between visits. Window for sessions during Weeks 3-10 is at least 2 days (minimum) and no more than 9 days (maximum) between visits. During Week 1 and Week 2, if an acupuncture session is missed, it may be made up the following week (there will be 3 sessions that following week). During Weeks 3-10, no sessions will be made up if missed.

³ Questionnaires at Midpoint and Endpoint should still be collected even if subject decides to discontinue the acupuncture sessions but is willing to stay on study. Week 1 for the control group begins at Randomization.

⁴ Acupuncture Expectancy Scale questionnaire to be collected only from subjects on Intervention (Acupuncture) arm at any time AFTER Randomization has occurred, but PRIOR to first acupuncture session.

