⁵ For acupuncture arm, Midpoint occurs at Week 5 ± 1 week from first acupuncture session, with Endpoint occurring at Week 10 ± 1 week from first acupuncture session. For control arm, Midpoint occurs at Week 5 ± 1 week from Randomization with Endpoint occurring at Week 10 ± 1 week from Randomization.

⁶ Collect MM date of diagnosis and staging at Baseline

⁷ If a subject decides or needs to be withdrawn from the study early (all visits and acupuncture assessments, if applicable), but is willing to complete an Early Termination visit, subject will complete assessments a final time, and will be considered Off Study (See section 8.2). Subjects do not need to complete questionnaires if they have done so within the last 2 weeks.

⁸ AESIs should only be collected on subjects randomized to acupuncture arm, beginning with first acupuncture session until 30 days after final acupuncture session.

⁹ For collection of opioid medication intake and concomitant medications, collect what has been taken over the past 7 days.

¹⁰ Collect chemotherapy regimen information throughout the study (if applicable).

¹¹ CIPN Neuropathy 0-10 & neuropathy physical location questionnaire is to be completed the first time **after consenting and prior to any other baseline procedures or assessments** to determine if the subject qualifies for enrollment into the study (see section 7.1.1).

¹² Notify subject of their randomization result.

¹³ Follow Up on AESIs: Can be done over the phone- this follow up for AESIs is only for subjects randomized to Acupuncture treatment arm.

¹⁴ Questionnaire may be completed after consent and prior to or after Randomization

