11.2 Sample Size

This study is designed with a primary objective to evaluate the effectiveness of acupuncture versus standard subject management in terms of reduction of neuropathy in actively treated multiple myeloma subjects diagnosed with CIPN. A Fisher's Exact Test with a two-sided alpha = 0.20 significance level will have at least 80% power to detect the difference between a standard of care group proportion of 0.10 and a treatment group proportion of 0.35 when the sample sizes are at least 22 and 44 evaluable subjects, respectively. In order to identify at least 66 evaluable subjects, we anticipate enrolling 75 subjects.

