11.4 Analysis Populations

The intent to treat (ITT) population will consist of all randomized subjects. The ITT population will be used to summarize the CONSORT diagram, subject disposition, and baseline subject disease characteristics. The evaluable population will consist of enrolled subjects who have complete baseline and Week 10 (\pm 1 weeks) neuropathy scores. The evaluable population will be

used for the analyses of all primary and secondary endpoints. Additionally, an intervention-compliant population will be defined as all subjects in the evaluable population who meet all of the following criteria:

- Subjects randomized to the acupuncture arm who have received at least 75%, or 9 of the 12 sessions in up to 13 weeks from randomization.
- Subjects randomized to the control arm who have not received any acupuncture at any time while they are on study.

The intervention-compliant population will be utilized for sensitivity analyses.

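### The primary score asks about neuropathy at the moment of answering, but completing it before a same-day acupuncture session is only preferred, so short-lived post-needling relief can count as Week 10 response in one arm

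*Combined protocol and SAP*

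**What the plan says.** Section 5.4.2 defines the primary measure as subject-reported global neuropathy "right now, measured on an 11-point scale". It has no recall period. The FACT-GOG-NTX, by contrast, uses seven days (5.4.4).

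On timing, Section 5.4 says "Questionnaires will be administered privately, preferably" before the acupuncture session for the intervention arm. No section makes this mandatory or sets a minimum interval after needling. Section 7.1.2, which describes the Midpoint and Endpoint visits, adds no rule on order.

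The primary endpoint (11.3.1) is a drop of two or more points from baseline to Week 10, within one week either side. The evaluable population (11.4) takes any subject with a baseline score and an in-window score. The primary analysis (11.5.4) is a Fisher exact test, with a supporting logistic regression that adjusts for baseline factors only.

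Section 1.1.4 describes a case series of five patients who all "received immediate BIPN-related pain reduction after a single acupuncture treatment". Lasting relief is reported for two of the three who had at least three sessions.

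For the intervention-compliant set, Section 11.4 requires "9 of the 12 sessions in up to 13 weeks from randomization". The dose-response analysis (11.3.4, 11.5.7) uses the number of sessions attended. Neither refers to the date of the Week 10 score. Session dates are documented (7.1.4).

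**The concern.** A question about the present moment, answered minutes after needles are removed, measures the immediate effect of that session together with whatever the course has achieved. The protocol's own background distinguishes immediate from lasting relief; the primary endpoint as collected cannot. The control arm has no session and so cannot show a matching effect, and the trial is open-label with a self-reported outcome (4.1). Any such contribution would be read as Week 10 benefit of the course.

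A smaller, related matter concerns session counts. A session attended after the Week 10 score cannot have influenced that score. Yet it can move a subject across the nine-session line into the compliant set, or into a higher dose category.

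**Working it through.** **1. Reproduce the design figure.** Section 11.2 states that a "two-sided alpha = 0.20 significance level will have at least 80% power" for 0.10 versus 0.35, with 22 control and 44 acupuncture subjects. I enumerated all 23 × 45 possible outcomes and rejected where the two-sided Fisher p-value was at most 0.20. Power is 81.7%, which agrees with the plan.

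**2. Baseline error rate.** With a true response of 0.10 in both arms, the same test rejects in 12.5% of trials. It rejects in favour of acupuncture in 5.2%.

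**3. Add post-session scores.** Let s be the share of acupuncture Week 10 scores taken after a session. Let t be the probability that such a score shows a drop of two or more points. With no lasting effect, the acupuncture response rate is

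p = (1 − s) × 0.10 + s × t.

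Example: s = 0.30 and t = 0.35 give 0.70 × 0.10 + 0.30 × 0.35 = 0.175.

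Neither s nor t is in the documents. I take t = 0.20 as a modest value and t = 0.35 as a high one (equal to the full design response), with s from 10% to 50%. The chance columns give the exact probability that the planned test is significant in favour of acupuncture, with control at 0.10.

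| s | p if t = 0.20 | chance | p if t = 0.35 | chance |
|---|---|---|---|---|
| 0% | 10.0% | 5.2% | 10.0% | 5.2% |
| 10% | 11.0% | 6.7% | 12.5% | 9.2% |
| 20% | 12.0% | 8.3% | 15.0% | 14.6% |
| 30% | 13.0% | 10.1% | 17.5% | 21.7% |
| 50% | 15.0% | 14.6% | 22.5% | 39.8% |

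**4. Check whether anything downstream removes the effect.** The endpoint definition, the evaluable population and the regression contain no term for time since the last session. The compliant-population sensitivity analysis selects on number of sessions, not on when the score was taken. The Week 5 analysis (11.5.5) uses scores collected under the same preference.

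**5. Sessions after the score.** Take a subject with eight sessions at the time of an early in-window score who then attends one more within 13 weeks of randomization. That subject has nine and enters the compliant set. In the dose groups of 11.5.7, one later session moves a subject from 7 to 8 (medium to high) or from 11 to 12 (high to complete).

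**The case against.** The strongest reply is that the protocol already states the right preference, and emphasises it, so few scores may be post-session. That is fair. With t = 0.35 and only 5–10% of scores affected, the chance is 7–9%, not far above 5%. The case series is also thin: five patients, pain rather than the 0–10 neuropathy item, and no two-point threshold. Both points limit the size of the concern. Neither closes the route, since a preference leaves compliance unknown and the text does not say that completion time relative to a session is recorded. The case report form is not in the documents, so it may capture this.

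Three stronger readings are tempting, and the documents do not support them.

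- *The Endpoint window inflates response because it opens before the course ends.* The acupuncture arm is assessed "with Endpoint occurring at Week 10 ± 1 week from first acupuncture session". Counted in week numbers, the window opens in Week 9; counted as elapsed time (day 70 ± 7), it opens on day 63, in Week 10. On either reading, a score before the last session reflects less treatment. If acupuncture works, that would tend to count against it.
- *The session-gap limits let the course run well beyond ten weeks.* Chaining the Weeks 3–10 limit of "no more than 9 days (maximum) between visits" might suggest this. The gap limits apply together with fixed weekly slots: two sessions a week in Weeks 1–2 and one a week in Weeks 3–10. A missed Week 1–2 session may be made up only in the following week, and later ones not at all.
- *Questionnaire mode differs by arm by design.* Section 5.4 says "The form of questionnaire administration will be based on the appointment situation", and only one arm has session visits. But all subjects have the same options, and controls may also attend clinic for myeloma care. The text supports only that mode is not standardised and may differ between arms.

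The 13-week limit is itself coherent: up to 2 weeks to the first session, plus 10 weeks, plus 1 week of window, makes 13. The gap is only that it is not tied to each subject's score date.

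**Conclusion.** The concern holds in a limited form. The plan permits the primary score to be taken just after needling in the only arm that is needled. The item asks about the present moment, and nothing in the stated analysis detects or removes such scores. Any resulting bias favours acupuncture if needling gives short-lived relief.

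Its size is not known from the documents. For post-session shares of 10% to 50%, the chance of a result favouring acupuncture when there is no lasting effect goes from 5% to 7–15% (20% responding on a post-session score) or to 9–40% (35% responding). These figures rest on assumed shares and rates, a 10% true response in both arms, and the planned test at 22 versus 44. The upper end needs both assumptions to be unfavourable.

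The session-count point is secondary. It affects a sensitivity population and an exploratory analysis, not the primary test. The sample size calculation is unaffected.

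**What to change.** 1. In Section 5.4, replace the preference with a requirement that Midpoint and Endpoint questionnaires be completed before any session held that day, whatever the mode. Repeat this in 7.1.2 and the study calendar.
2. Record whether each questionnaire was completed before or after a same-day session, and the time.
3. Keep a late-completed score in the evaluable population, and add to 11.5.4 a sensitivity analysis of the primary endpoint that excludes post-session scores. This avoids spending the allowance of 75 − 66 = 9 subjects on timing deviations.
4. In 11.4 and 11.5.7, count only sessions attended before the Week 10 score, using the session dates already documented. A subject scored just before the twelfth session then counts as 11, so the labelling of the complete-dose category needs a sentence.

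Optionally, record the mode of completion, since it is not standardised. The Endpoint window and session schedule need no change for this point.

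The cost is wording in a few sections, one or two form fields and slightly less scheduling flexibility on session days. Treatment and sample size stay as planned.
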